CLINICAL TRIAL PROTOCOL SYNOPSIS

Name of company:		Boehringer Ingelheim	
Name of finished product:		Not applicable	
Name of active ingredient:		BI 655064	
Protocol date: 29 Oct 2015	Trial number: 1293.10		Revision date: 07 SEP 2018
Title of trial:	A double-blind, randomised, placebo-controlled trial evaluating the effect of BI 655064 administered as sub-cutaneous injections, on renal response after one year of treatment, in patients with active lupus nephritis		
Coordinating Investigator:			
Trial site(s):	Multi-centre trial in approximately 22 countries		
Clinical phase:	II		
Objective(s):	To characterize the dose-response relationship, identify the target dose and investigate the safety, tolerability and efficacy of three doses of BI655064 given s.c. for 52 weeks in patients with Lupus Nephritis		
Methodology:	Multi-national, randomized, double-blind, placebo-controlled, 4 parallel group in patients with Lupus Nephritis		
No. of patients:			
total entered:	120 randomised		
each treatment:	20 pat in group 1 (120mg) 20 pat in group 2 (180 mg) 40 pat in group 3 (240 mg) 40 patients in placebo group		
Diagnosis :	Lupus Nephritis (Class III or IV (ISN/RPS 2003 classification))		

Name of company:		Boehringer Ingelheim	
Name of finished product:		Not applicable	
Name of active ingredient:		BI 655064	
Protocol date: 29 Oct 2015	Trial number: 1293.10		Revision date: 07 SEP 2018
Main criteria for inclusion:	
1. Males and females, age 18 –70 (inclusive) years at visit 1
 
2. Diagnosis of systemic lupus erythematosus (SLE) by ACR criteria 1997, at least 4 criteria must be documented, one of which must be a positive anti-dsDNA antibody OR a positive antinuclear antibody (ANA) at screening or around time of start of induction therapy
 
3. Lupus Nephritis Class III or IV (ISN/RPS 2003 classification) with either active or active/chronic disease, co-existing class V permitted, proven by renal biopsy within 3 months prior to screening or during screening in case induction therapy for LN has not yet been started
 
4. Active renal disease evidenced by proteinuria ≥ 1.0 g/day (Uprot/Ucrea ≥ 1)
		
Test product(s):	BI 655064		
dose:	
Dose group 1: 120 mg once a week for 3 weeks followed by 120 mg once every two weeks
 
Dose group 2: 180 mg once a week for 3 weeks followed by 180 mg once every two weeks
 
Dose group 3: 240 mg once a week for 3 weeks followed by 120 mg once a week
		
mode of administration:	Subcutaneous injection		
Comparator products:	Placebo		
dose:	Not applicable		
mode of administration:	Subcutaneous injection		
Duration of treatment:	52 weeks		

Name of company:		Boehringer Ingelheim	
Name of finished product:		Not applicable	
Name of active ingredient:		BI 655064	
Protocol date: 29 Oct 2015	Trial number: 1293.10		Revision date: 07 SEP 2018
Endpoints	
Primary endpoint : Proportion of patients with Complete Renal Response at week 52
 
Secondary endpoints :
 
Proportion of patients with Complete renal response at week 26
 
Proportion of patients with Partial renal response at week 26 and 52
 
Proportion of patients with Major renal response at week 26 and 52
		
Safety criteria:	Physical examination, vital signs (BP, PR), weight, 12-lead ECG, laboratory tests, adverse events and tolerability		
Statistical methods:	The primary objective is to define a suitable dose for BI 655064 regarding efficacy and safety for further pivotal testing in Phase III. For this purpose, a multiple comparison procedure with modelling (MCPmod) approach is considered. The primary endpoint is Complete Renal Response after 52 weeks of treatment. Comparisons between treatment groups will be exploratory in nature and based on the numerical comparison of the respective response rates including confidence intervals when appropriate.		

FLOW CHART

Trial Periods	Screening	Randomised Treatment Period (week 0 – 26)											
		1	2	2.1	2.2	3	4	5	6	7	8	9	10
Visit	1	2	2.1	2.2	3	4	5	6	7	8	9	10	11
Day	-28 to -	1	2 ¹	3 ¹	8	15	29	43	57	85	113	148	18
Week	-4 to -1	0			1	2	4	6	8	12	16	21	26
Time window for visits (days)	N.A.	±0	±0	±0	±1	±1	±2	±2	±3	±3	±5	±5	±3
Check of Eligibility	X	X											
Informed Consent	X												
Med. History / Demographics	X												
Physical Examination ²	X ^c	X ^c			X ^t	X ^t	X ^t	X ^t	X ^t	X ^c	X ^t	X ^t	X ^c
12-Lead Resting ECG		X					X			X			X
Inclusion/Exclusion Criteria	X	X											
Randomisation		X											
Administer BI 655064/placebo ³		X			X	X	X	X	X	X	X	X	X
Administer Methylprednisolone 500mg i.v. (SOC I) ¹		X	X	X									
Start oral glucocorticoids ⁴				X									
Administer MMF 2-3g/day													
Dispense treatment and instructions for home admin ⁵						X	X	X	X	X	X	X	X
Assess compliance							X	X	X	X	X	X	X
Assess for Adverse Events		X	X	X	X	X	X	X	X	X	X	X	X
Concomitant Therapy	X	X	X	X	X	X	X	X	X	X	X	X	X
Safety Laboratory Tests ⁶	X	X			X	X	X	X	X	X	X	X	X
2 x 24h collection of urine		X											X
Uprot/Ucrea spot urine	X	X			X	X	X	X	X	X	X	X	X
Serum pregnancy test ⁷ (only female subjects)	X												
Urine Pregnancy Test ⁷		X					X		X	X	X	X	X

Trial Periods	Screening Period	Randomised Treatment Period (week 0 – 26)											
		2	2.1	2.2	3	4	5	6	7	8	9	10	11
Visit	1	2	2.1	2.2	3	4	5	6	7	8	9	10	11
Day	-28 to -7	1	2 ¹	3 ¹	8	15	29	43	57	85	113	148	183
Week	-4 to -1	0			1	2	4	6	8	12	16	21	26
Time window for visits (days)	N.A.	±0	±0	±0	±1	±1	±2	±2	±3	±3	±5	±5	±3
Infectious Serology, TB Screening	X												

Trial Periods	Randomised Treatment Period (week 27 – 52)					Follow-up Period ¹¹	
Visit	12	13	14	15	16-EOT ¹⁰	17	18-EOS
Day	211	246	281	323	365	393	421
Week	30	35	40	46	52	56	60
Time window for visits (days)	±5	±5	±5	±5	±3	±5	±5
Physical Examination ²	X ^t	X ^t	X ^c	X ^t	X ^c	X ^t	X ^t
12-Lead Resting ECG			X		X		
Administer BI 655064/placebo ³	X	X	X	X			
Assess compliance	X	X	X	X	X		
Continue oral glucocorticoids ⁴	→						
Continue MMF 1-2g/day	→						
MMF level					X		
Dispense treatment and instructions for home admin ⁵	X	X	X	X			
Assess for Adverse Events	X	X	X	X	X	X	X
Concomitant Therapy	X	X	X	X	X	X	X
Safety Laboratory Tests ⁶	X	X	X	X	X	X	X
2 x 24h collection of urine					X		
Uprot/Ucrea spot urine	X	X	X	X	X	X	X
Urine Pregnancy Test ⁷	X	X	X	X	X	X	X

Trial Periods	Randomised Treatment Period (week 27 – 52)					Follow-up Period ¹¹	
Visit	12	13	14	15	16-EOT ¹⁰	17	18-EOS
Day	211	246	281	323	365	393	421
Week	30	35	40	46	52	56	60
Time window for visits (days)	±5	±5	±5	±5	±3	±5	±5

Optional renal biopsy					X		
Vital status collection							X ¹²
Conclusion of patient participation							X

Footnotes:

1. Visits 2.1 and 2.2 are necessary for IV steroids injections only. Refer to [section 4.2.1](#). IV methylprednisolone injections to be done only to reach 1.5 g total dose if not reached within 6 weeks prior to randomisation. If a higher dose of IV steroid is considered necessary by the investigator a total dose of up to 3g is acceptable.
2. Physical exam includes height (at screening only), vital signs and weight. x^c is a complete physical examination, x^t is a targeted physical examination. See [section 5.3.1](#) for description.
3. PK samples will be collected before study medication administration on these days if the visit date coincides with a day of injection; therefore study medication should be administered on site in that case. If the visit does not correspond to an injection day, the PK sample will be taken at anytime during the visit. Exact date and time of sampling should be recorded. See [Section 5.4](#)
4. Oral glucocorticoids have to be started on day 4 (or day 1 if IV steroids were already received) and tapered to 10mg prednisone equivalent within 12 weeks.
5. Starting from week 2, patients have to administer the injections with BI 655064/placebo by themselves always 7 days after the previous dose.
6. Safety lab tests : details of tests is given in [section 5.3.3](#)
7. Pregnancy test will be performed in women of childbearing potential every 4 weeks. A serum pregnancy test will be performed at screening visit. Urine dipstick tests will be done during the screening phase (8-10 days after the first test) and immediately before starting medication. It will be repeated at visits every 4 weeks and will be provided for at home pregnancy testing as soon as visit intervals are > 4 weeks,. In case of a positive urine pregnancy test result, a blood sample for serum pregnancy test will be drawn for confirmation. Only those females with a negative pregnancy test will receive study medication and will be allowed to start treatment with MMF
8. Will be measured in serum and urine
9. Questionnaires should be completed in the following order: LupusPRO, SF-36, FACIT-F, before any other visit assessment
10. EOT visit has to be carried-out for all patients when they stop treatment. At week 52, patients who reach at least partial response (based on values obtained at week 46) will be offered to enter a maintenance trial (trial 1293.13). Patients who stopped treatment before week 52 will not be allowed to participate in the maintenance trial.
11. Follow up visits to be performed after end of treatment except for patients entering the maintenance trial 1293.13 and patients who have withdrawn drug prematurely
12. For randomized patients leaving the study before the planned EOS, their vital status should be collected at week 60

TABLE OF CONTENTS

TITLE PAGE	1
CLINICAL TRIAL PROTOCOL SYNOPSIS	2
FLOW CHART	5
TABLE OF CONTENTS	9
ABBREVIATIONS	12
1. INTRODUCTION.....	15
1.1 MEDICAL BACKGROUND	15
1.2 DRUG PROFILE	16
2. RATIONALE, OBJECTIVES, AND BENEFIT - RISK ASSESSMENT	18

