	Creatinine and calculated Creatinine Clearance (CKD-EPI) Bilirubin Total, Bilirubin Direct and indirect Albumin, Uric Acid, Urea nitrogen	Screening, Day 1/8 then every visit until EOT (included), repeat after EOT only if clinical significant findings at discretion of investigator.
	Cholesterol, triglycerides	baseline + every 4 weeks §
	hsC-Reactive Protein	baseline /w4/8/12/26/35/52
	Haptoglobin	baseline + week 12/26/52
Serum Pregnancy test *	Human Serum Chorionic Gonadotropin	Screening + anytime if urinary test positive
Urine Pregnancy test (only for females of childbearing potential)*	Human Chorionic Gonadotropin in the urine	Screening phase + baseline + every 4 weeks
Urinalysis - dipstick	Urine: Nitrite, Protein, Glucose, Ketone, Bilirubin, RBC/ Erythrocytes, WBC/ Leukocytes, pH, creatinine Urobilinogen	Screening, Day 1/8 then every visit until EOT (included), repeat after EOT only if clinical significant findings at discretion of investigator
Urine	Spot protein/creatinine ratio £	Every visit
Urine-Sediment (microscopic examination,)	Urine: Sediment Bacteria, Cast in Sediment, Squamous Epithel Cells, Sed. Crys., Unspecified, Sediment RBC/ Erythrocytes, Sediment WBC/ Leucocytes	baseline + week 4, 8 and every visit until EOS or if urine analysis abnormal according to investigator (reflex test)
Immunology testing	Total IgG and IgM	baseline + week 12/26/40/52
	ANA,	Screening, Baseline, week 26 and 52
	Anti-ds-DNA, complement C3, C4 anti-C1q antibodies Anti-phospholipid antibodies	Screening, Baseline + week 4/8/12/16/26/30/40/52/EOS
Infections screening,**	Hepatitis B Surface Antigen (qualitative) Hepatitis B core Antibody Hepatitis C Antibodies (qualitative) HIV-1 and HIV-2 Antibody (qualitative) QuantiFERON-TB Gold [#]	Screening only

* Urine (dipstick) pregnancy test will be conducted prior to first study medication administration. In case of a positive urine pregnancy test result, a blood sample for serum pregnancy test will be drawn for confirmation. Only those females with a negative pregnancy test will receive study medication.

** Results of infections screening will not be captured in the sponsor's database

In case HbC positive but HBs antigen negative then measure Hepatitis B DNA: if positive exclude patient, if negative patient can be included

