6. INVESTIGATIONAL PLAN

6.1 VISIT SCHEDULE

For a detailed overview of the trial procedures and time windows for visits, please refer to the [Flow Chart](#).

The trial consists of a screening visit followed by a one year treatment period and 2 follow-up visits.

The study will last until every evaluable entered patient has completed the last follow-up visit.

After giving his/her Informed Consent, the patient will be screened for inclusion and exclusion criteria for the study at visit 1. Visit 2 will be scheduled after visit 1, after results from central laboratory are obtained (a minimum of 7 days to be planned). The screening phase must not be longer than 4 weeks (from visit 1 to visit 2). The patient will be randomised at visit 2 if all inclusion and none of the exclusion criteria are fulfilled.

Windows of ± 1 to ± 5 days is allowed for a majority of visits, to accommodate scheduling problems. If a delay is observed for a particular visit, the original calendar schedule should be kept for subsequent visits (delays should not accumulate). If a visit is missed the patient should be instructed to come for a visit as soon as possible. Investigator should contact the BI monitor to discuss further schedule.

Follow up visits have to be organized at 4 and 8 weeks after End of treatment

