6.2 DETAILS OF TRIAL PROCEDURES AT SELECTED VISITS

6.2.1 Screening and run-in period(s)

Screening Period

Written informed consent must be obtained before any protocol specific screening assessments are performed.

The screening visit should take place within 7-28 days prior to randomization (Visit 2). All study procedures and assessments including the repeated tests in determining the patient's eligibility must be available prior to Visit 2.

Patients must satisfy all inclusion and exclusion criteria prior to randomization (Visit 2).

Details of any patient who is screened for the study but is found ineligible must be entered in an enrolment log (see ISF) and documented in the eCRF.

It is allowed to re-test (once) a lab parameter that is found abnormal at visit 1 if it is thought to be a measurement error (i.e. there was no abnormal result of this test in the recent history of the patient and there is no related clinical sign)".

It is allowed to re-test the proteinuria if the result from spot ratio at screening visit does not correspond to recent measurements done at site. In that case it is preferred to do a 24h measurement.

For a detailed description of the trial procedures at the screening visit, refer to [Flow Chart](#).

Baseline Conditions/Medical history:

As a precaution, risk factors for thromboembolic disease (including medical history of DVT/TE) should be specifically checked. If clinically relevant, the case should be discussed with the TCM/TMM prior to randomization. History of antiphospholipid syndrome should be recorded and patients should be excluded from the study.

Pregnancy tests:

Serum pregnancy test will be performed at screening visit. A urine dipstick test will be done during the screening phase and immediately before starting medication. In case of a positive urine pregnancy test result, a blood sample for serum pregnancy test will be drawn for confirmation. Only those females with a negative pregnancy test will start treatment with MMF and will receive study medication.

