6. GENERAL ANALYSIS DEFINITIONS

6.1 TREATMENTS

For reporting purposes, all randomised patients will be classified into one of the following treatment groups:

Sort order	Treatment	Long label	Short label
01	B	BI 655064 120mg	BI 120mg
02	C	BI 655064 180mg	BI 180mg
03	D	BI 655064 240mg	BI 240mg
04	A	Placebo	Placebo

These will be the default labels and sort order for reporting the treatment groups.

The following study periods based on actual start and stop dates of study treatment administration are defined:

Screening: day of informed consent to day prior to the start of randomised medication

Treatment: start date of randomised double-blind medication to date of last dose

Follow-up: day after the last dose of randomised double-blind medication through trial completion and after trial completion

Rules for assigning AEs/laboratory data to the study periods are as follows.

AEs/laboratory data will be assigned to the treatment period if they occur/samples were taken after the first injection of study medication to the date of last administration of study medication plus 50 days.

Since AE onset time was not recorded, investigators were asked to provide more information for AEs with date of onset equal to date of first injection. Additional information was to be provided in the AE comment field. The trial team will review the comments & will impute a time to capture onset as prior to or following first injection of study medication. An analysis data set will be created to incorporate this information. If the site indicates that the AE onset time is prior to trial medication administration then the AE will be assigned to the screening period. If the site indicates that the AE onset time is after trial medication administration or there is no information regarding onset then the AE will be assigned to the treatment period.

Adverse events with onset on or after the 51st day after the last administration of trial medication will be considered 'Follow-up' events. However, if the patient rolls over to the extension trial (1293.13) & receives the first dose of trial medication in 1293.13, any new events or worsening of existing events will be assigned to the treatment period of 1293.13.

Laboratory data on or after the 51st day after the last administration of trial medication will be considered 'Follow-up' data.

Proprietary confidential information © 2020 Boehringer Ingelheim International GmbH or one or more of its affiliated companies

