6.7 BASELINE, TIME WINDOWS AND CALCULATED VISITS

Study day will be calculated relative to the date and time of the first dose of double-blind randomised treatment. The day prior to the start of double-blind randomised treatment will be ‘Day -1’ and the day of the start of double-blind randomised treatment will be ‘Day 1’; therefore ‘Day 0’ will not exist.

Unless otherwise specified, baseline is defined as the latest time-point on or before the date of the first randomised treatment administration (the date of the first dose is acceptable because the first dose of medication is to be taken in clinic on the day of randomisation AFTER all

Proprietary confidential information © 2020 Boehringer Ingelheim International GmbH or one or more of its affiliated companies

baseline assessments have been made.) If there is no measurement for a particular variable on or before the date of first randomised treatment administration then no baseline will be derived for that variable.

The following visit labels will be used in all tables & graphics. As specified in the CTP, EOT refers to the End of Treatment visit. EOS is the End of Study visit. FU is Follow Up.

For discontinued patients (only):

EOT = 'EOT'

For completed patients who do not roll over to trial 1293.13:

Week 52='Week 52/ EOT'

Week 56='FU'

Week 60='EOS'

For completed patients who roll over to trial 1293.13:

Week 52='Week 52/ EOT'

For patients who discontinue trial drug but continue participation in trial:

EOT='EOT'

Visit 5='Visit 5/FU'

Visit 8='Visit 8/FU'

Visit 11='Visit 11/FU'

Visit 14='Visit 14/FU'

EOS ='EOS/FU'

Visit labels containing 'Visit' or 'FU' occurred after the EOT visit; patient was not on drug for these visits.

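### At the permitted 7-day minimum screening, the repeat pregnancy test due 8-10 days after the first cannot be done before first dose, and the flow-chart grid shows no screening-phase urine test

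*Protocol*

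**What the plan says.** **Tests.** Footnote 7 to the protocol flow chart sets three pregnancy tests before treatment in women of childbearing potential. The first is at Visit 1: "A serum pregnancy test will be performed at screening visit". The other two are urine tests: "Urine dipstick tests will be done during the screening phase (8-10 days after the first test) and immediately before starting medication". The footnote makes a negative test a condition for study drug and for starting MMF.

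**Screening length.** Section 6.1 says of the gap between Visits 1 and 2: "a minimum of 7 days to be planned". Section 6.2.1 gives the range: "The screening visit should take place within 7-28 days prior to randomization (Visit 2". The flow chart puts Visit 1 between Day -28 and Day -7 and Visit 2 on Day 1, with a window of zero days.

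**Where else the urine test appears.** The grid row labelled "Urine Pregnancy Test ⁷" is empty at Visit 1; its first mark is at Visit 2 and its next at Visit 5. Table 5.3.3:1 gives the frequency as "Screening phase + baseline + every 4 weeks". Section 6.2.1 also requires a urine test during screening and another before medication. Neither of these two places states the 8-10 day interval.

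**Day counting.** SAP 6.7 fixes the numbering: "The day prior to the start of double-blind randomised treatment will be" Day -1, the first-dose day is Day 1, and there is no Day 0. SAP 6.1 defines the period as: "Screening: day of informed consent to day prior to the start of randomised medication".

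**The concern.** The interval in footnote 7 is longer than the shortest screening the protocol allows, and nothing in the text links the two. A site that books Visit 2 at the minimum has followed sections 6.1 and 6.2.1 and the flow chart, yet cannot carry out the footnote's repeat test before dosing.

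The layout makes this easy to overlook. No visit lies between Visits 1 and 2. The footnote offers home testing only once visits are more than 4 weeks apart, whereas section 6.1 caps screening at 4 weeks. A site working from the grid, from Table 5.3.3:1 or from section 6.2.1 would not meet the 8-10 day interval at all. The negative-test condition does not say which tests must be negative, so it can be read as satisfied without the spaced one.

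At stake is a repeat test that the sponsor added in global amendment 2 because of new MMF labelling, in a protocol that itself names MMF's teratogenicity.

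**Working it through.** **Inputs.** Interval from first test to repeat test: k = 8, 9 or 10 days (footnote 7). First test: the Visit 1 serum test (footnote 7). Screening length: s = 7 to 28 days (sections 6.1 and 6.2.1). First dose: Visit 2, Day 1. No Day 0 (SAP 6.7).

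**Reproducing the plan's own range.** Without a Day 0, Day -7 to Day 1 is 7 days and Day -28 to Day 1 is 28 days, which matches the 7-28 days of section 6.2.1. With a Day 0 the gaps would be 8 and 29 days, which would not match, so the no-Day-0 count is the consistent one.

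**Date of the repeat test.** For screening length s, a test k days after Visit 1 falls on Day k - s + 1 when k is at least s, and on Day -(s - k) when k is smaller than s.

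| Screening length s | k = 8 | k = 9 | k = 10 | Possible by the Visit 2 date | Possible strictly before it |
|---|---|---|---|---|---|
| 7 | Day 2 | Day 3 | Day 4 | none | none |
| 8 | Day 1 | Day 2 | Day 3 | 8 | none |
| 9 | Day -1 | Day 1 | Day 2 | 8, 9 | 8 |
| 10 | Day -2 | Day -1 | Day 1 | 8, 9, 10 | 8, 9 |
| 11 | Day -3 | Day -2 | Day -1 | 8, 9, 10 | 8, 9, 10 |

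**Reading the table.**

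- At 7 days no date in the interval precedes the first dose. The pre-dose test comes 7 days after the first test, one day short of the interval.
- At 8 days the only usable date is Day 1. A test that day can precede the dose, but it coincides with the pre-dose test and lies outside screening as SAP 6.1 defines it.
- At 9 days a separate test first fits, on Day -1.
- From 11 days the whole interval fits before Visit 2.

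**Count of lengths.** 28 - 7 + 1 = 22 permitted lengths. One (7 days) rules out the spaced test before dosing; one more (8 days) rules out only a separate spaced test; 22 - 2 = 20 allow both tests separately.

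**Grid check.** In the same grid the serum-test row is marked at Visit 1 and the urine-test row is not, so the empty urine cell is not explained by a shifted column.

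**The case against.** The best defence is that 7 days is a floor and not a target. Nothing obliges a site to book Visit 2 that early, and section 6.2.1 wants the assessments that decide eligibility, repeat tests included, to be available before Visit 2. On that reading a site with the second test outstanding simply schedules Visit 2 later, and every rule is met at 9 days or longer. This stands: a reader might infer that sites are forced into a breach, and they are not. What remains is that the protocol expressly allows 7 days and never says that the test interval governs for these patients.

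A second defence is that very short screenings may be rare. Section 6.1 makes Visit 2 wait for central laboratory results, and the rationale for global amendment 1 mentions up to 21 days for anti-dsDNA. But the current inclusion criterion also accepts a result from around the start of induction therapy, so that turnaround sets no floor. The documents give no frequency either way.

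A third is that the test is not missing from the flow chart, because footnote 7 is attached to the urine row. That is right. Only the grid mark is absent, and Table 5.3.3:1 and section 6.2.1 both require a screening-phase test. The gap is in timing and visibility, not in the existence of the requirement.

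**Conclusion.** The inconsistency is real and narrow. At the 7-day minimum the spaced test cannot precede the first dose; at 8 days it can, but only by merging with the pre-dose test. Together with the unmarked grid and the two places that omit the interval, this means the spaced repeat test can be missed.

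Two stronger readings are tempting and are not supported:

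- **That the test is impossible before dosing at 8 days as well.** It can be done on Day 1.
- **That the MMF safeguard as a whole can be missed.** At every screening length the Visit 1 serum test, the pre-dose urine test and the negative-test requirement remain, as does the two-method contraception criterion. What can be lost is the spacing, by one day at the minimum. Visit 2 is also not the start of MMF for everyone, since section 6.2.2 notes that some patients begin induction earlier.

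The conclusion assumes that the footnote's first test is the Visit 1 serum test and that days are counted without a Day 0. The 8-day observation also leans on the SAP's definition of screening, which serves to assign data to periods and is not a site instruction. The figures of 1 and 2 out of 22 count calendar options, not patients. No endpoint, analysis or statistical figure changes.

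**What to change.** Reconcile footnote 7, the flow-chart urine row, Table 5.3.3:1 and sections 6.1 and 6.2.1, so that the test interval and the minimum screening length can both be met for women of childbearing potential. State the timing identically wherever the screening-phase test is mentioned, and show that test in the grid. Which rule moves is for the sponsor; this review takes no position on the right interval or screening length.

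The cost is a text amendment and, depending on the sponsor's choice, possibly one or two extra screening days for some patients.
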